4 Introduction

This document is a protocol for a human research study. This study will be carried out in accordance with the applicable United States government regulations and Mayo Clinic research policies and procedures.

4.1 Abstract

Neuromuscular blocking agents (NMBAs) are a commonly utilized class of medications in the perioperative setting that can help facilitate endotracheal intubation, optimize surgical conditions, and assist with mechanical ventilation. Experts recommend the use of quantitative (or objective) neuromuscular monitors whenever NMBAs are utilized because these devices are the only method for reliably determining adequate neuromuscular paralysis and recovery of neuromuscular function. Unfortunately, several barriers exist that have prevented the widespread application of these devices, and many practitioners are still using qualitative (subjective) methods (i.e., use a peripheral nerve stimulator) as an assessment of neuromuscular blockade despite the lack of accuracy of subjective methods and the well-described morbidity and mortality associated with residual blockade. Objective monitors may also prove useful during the onset of NMB and provide useful information about when optimal intubation conditions have been reached.

The primary aim of this study is to compare intubating conditions at varying levels of rocuronium-induced neuromuscular blockade.

The TetraGraph (Senzime AB, Uppsala, Sweden) is an FDA-approved standalone EMG-based quantitative monitor that measures electrical activity within the muscle following peripheral nerve stimulation and is unaffected by involuntary patient motion or restricted muscle movements from surgical positioning. Following standard of care administration of propofol between 1 and 1.5 mg/kg and lidocaine between 0.5 and 1 mg/kg intravenously (IV) for induction of general anesthesia, the TetraGraph neuromuscular monitor will be calibrated, following which rocuronium at 0.6 mg/kg will be administered. Intubation will commence based on the one of two triggers based on randomization has been reached. One group will be intubated once the train-of-four count (TOFC) reaches 1 and the other when 2 minutes have passed. The time to intubation will be recorded and the intubating health care clinician will be surveyed about intubation conditions that includes variables such as: ease of laryngoscopy (jaw relaxation), vocal cord position and movement, airway reaction (coughing) and movement of the limbs ([Table 17.2](#)) The assessment will be done using video laryngoscopy display at the time of intubation.

4.2 Background

Neuromuscular blocking agents (NMBAs) are a class of medications routinely used during anesthesia to facilitate endotracheal intubation (1) and improve conditions for optimal surgery (2). However, these medications are also associated with respiratory complications in the early

postoperative period due to residual neuromuscular blockade (RNMB) (3-5). Even when neuromuscular blockade is reversed in the operating room, postoperative residual weakness continues to be a common problem in the post-anesthesia care unit (PACU), and a significant number of patients continue to arrive in the PACU with objective evidence of residual neuromuscular blockade (6, 7). While not every patient with residual weakness develops a postoperative complication, many can develop avoidable critical respiratory events (8, 9). Furthermore, special populations such as the elderly are at particular risk for developing complications related to postoperative residual weakness (10). The use of quantitative monitoring has been shown to reliably reduce the incidence of postoperative residual weakness and the ensuing complications (11-13).

Quantitative neuromuscular monitoring devices objectively measure residual weakness and display the results numerically. This is traditionally accomplished by performing a train-of-four (TOF) stimulation at the ulnar nerve and measuring the response of the adductor pollicis muscle. The degree of muscle weakness is determined by calculating the TOF ratio, which consists of the ratio of the fourth muscle contraction to the first. Adequate recovery that excludes clinically significant weakness from neuromuscular blockade is defined as a TOF ratio ≥ 0.9 , a measurement that can be determined reliably only with a quantitative monitor (14, 15). With an abundance of literature supporting the use of objective neuromuscular monitors, a panel of experts recently recommended the universal adoption of such devices whenever NMBA are utilized (16) however, quantitative monitors can be expensive and require additional training.

Electromyography (EMG) is a type of quantitative monitor that measure electrical activity, termed compound muscle action potentials (cMAPs) following nerve stimulation (typically at the adductor pollicis muscle after ulnar nerve stimulation) (17). As EMG measures cMAPs and does not require freely moving thumbs for accurate measurements, many experts have referred to this monitoring modality as the “new gold standard”. TetraGraph (Senzime AB, Uppsala, Sweden) is a standalone EMG-based device that is FDA-approved.

Many clinicians default to the suboptimal practice of subjective monitoring (18, 19), which refers to visual or tactile evaluation of the train-of-four (TOF) in response to neurostimulation provided by peripheral nerve stimulation. However, subjective evaluation may provide inaccurate information and assessment of full recovery compared to objective evaluation (20, 21). A consensus statement by the international panel of experts in neuromuscular blockade issued in 2018 state that subjective evaluation is not predictive of adequate neuromuscular recovery and is not sensitive to the presence of residual weakness. They state that their use should be abandoned in favor of objective monitoring, because after the TOFR recovers to >0.40 , anesthesia providers can no longer detect the presence of fade by subjective evaluation and they may assume a complete recovery from neuromuscular blockade, despite the presence of minimal levels of NMB (16). It is worth highlighting that after tracheal extubation, even minimal degrees of residual block is associated with impaired function of respiratory and pharyngeal muscles, upper airway obstruction (22), hypoxemia (23), and awareness during anesthesia (24).

Utilizing recommendations from the Good Clinical Practice (GCP) Guidelines for monitoring of neuromuscular function (25), we will compare intubation conditions at varying levels of

neuromuscular blockade utilizing EMG. Currently, our practice has significant heterogeneity in determining when the appropriate time to perform endotracheal intubation following induction of anesthesia. Following induction with propofol, rocuronium is administered and patients can have significantly varied response to this medication. Most providers wait approximately 2 minutes before intubating the patient's trachea. Given this drug's variable pharmacokinetics, quantitative monitoring may be used to objectively determine when optimal intubating conditions have been achieved. While use of these devices during induction of anesthesia represents best practice, it is rarely performed. In fact, it is very common to observe endotracheal intubation in a patient that has not yet had complete onset of neuromuscular blockade as evidenced by coughing or movement of the limbs following intubation. Further complicating the matter is that there is no method for objectively measuring the muscle groups that are important during intubation (oropharyngeal adductors and the diaphragm) and clinicians must make inferences about these muscle groups based on other muscle groups (adductor pollicis). Having a better understanding of the correlation between objective measurements at the hand and intubating conditions can provide anesthesia providers important information regarding the timing of endotracheal intubation.

4.3 Risks and Benefits

- Utilization of quantitative neuromuscular monitors is currently standard of care at Mayo Clinic. However, most providers place these devices after induction of anesthesia. Placing them prior to induction ensures they are working appropriately throughout the perioperative experience.
- Intubating the trachea at a TOFC=1 could result in conditions that suboptimal with movement of the vocal cords. However, the current standard of care involves intubating once about two minutes has elapsed and movement of the vocal cords is commonly seen. Whether the TOFC=1 or two minutes has elapsed, endotracheal intubation carries the risk of damage to the vocal cords. Utilization of the TOFC=1 represents a potential benefit to the patient as providers will have to use a quantitative neuromuscular monitor to determine intubation timing, rather than just intubating based on unclear, subjective endpoints.

5 Study Objectives

Primary Objective

Compare intubating conditions when patients are intubated at 2 different endpoints: TOFC=1 or 2 minutes after administration of rocuronium at 0.6 mg/kg (usual current clinical routine).

Secondary Objective

Correlate the ratio of the amplitude of the first twitch and control twitch (T_1/T_c) to intubating conditions.

6 Study Design

6.1 General Description

[figure not shown]
This unblinded, single center, prospective, randomized, study will involve 170 patients undergoing surgical procedure that involved administration of neuromuscular blockade agents intraoperatively in elective surgical procedures.

6.2 Number of Subjects

170

6.3 Duration of Participation

15 min at the start of the operation

6.4 Primary Study Endpoints

Compare intubating conditions when patients are intubated at 2 different endpoints: TOFC=1; or 2 minutes after rocuronium at 0.6 mg/kg. The assessment of the intubating conditions will be evaluated by the healthcare providers using a scale ([Table 17.1](#)) that includes 4 variables (ease of laryngoscopy, vocal cord position, and reaction to tracheal tube insertion with 3 response options

per each evaluation. The composite score (1-3) will be compared between groups, with the lowest total score of 3 correlating with optimal intubating conditions and the highest score of 9 representing the worse possible intubating conditions. The scale has been validated previously. (25)

6.5 Secondary Study Endpoints

The secondary endpoint is to evaluate intubating conditions as a function of the amplitude of the first twitch and control twitch (T_1/T_c).

6.6 Identification of Source Data

The study data points will be recorded on the developed Case Report Forms (CRFs) by the study team members. In addition to the data collected intraoperatively, several intraoperative characteristics will also be extracted from the medical record ([Table 17.2](#)).

7 Subject Selection Enrollment and Withdrawal

7.1 Inclusion Criteria

- Age $>$ or $=$ 18 years old
- Patients willing to participate and provide an informed consent
- Patients undergoing elective surgical procedures that require use of NMBA agents (rocuronium) administered intraoperatively.

7.2 Exclusion Criteria

- Patients with disorders, such as stroke, carpal tunnel syndrome, broken wrist with nerve damage, Dupuytren contracture, or any similar wrist injury.
- Patients with systemic neuromuscular diseases such as myasthenia gravis.
- Patients with significant organ dysfunction that can significantly affect pharmacokinetics of neuromuscular blocking and reversal agents, i.e., severe renal impairment or end-stage liver disease.
- Patients having surgery that would involve prepping the arm into the sterile field.
- Patients receiving a rapid sequence induction.

7.3 Subject Recruitment, Enrollment and Screening

On a daily basis, there are over 70 elective surgical cases performed at Mayo Clinic in Florida and thus no difficulties in accrual are anticipated based on historical volumes. We will target at least 10 participants per week to complete this study. The initial accrual period will last at least 3

months followed by interim analysis and additional time for accrual will be determined to meet the target. Patients will be provided with a Research Participant Consent and Privacy Authorization Form describing the study devices, protocol, inclusion and exclusion criteria, as well as risks and benefits of participation.

7.4 Early Withdrawal of Subjects

7.4.1 When and How to Withdraw Subjects

Patients are free to withdraw at any time and for whatever reason. If patient withdraws consent prior to arrival to operating room, the study data will not be collected. If patient withdraws consent after study data was already completed, the participant will need to provide instructions to the study team to remove his/her data from the data set. Pre-specified reasons for discontinuing include, but are not limited to, the following:

- Patient Request: Patient decided that he/she did not want to continue (for any reason)
- Adverse Event: Patient experienced a related or unrelated event that would interfere with the study objectives/evaluation
- Inclusion/Exclusion Discrepancy/Violation: Patient should not have been enrolled
- Other: Any other reason

7.4.2 Data Collection and Follow-up for Withdrawn Subjects

If a Participant withdraws from the study, no additional attempts will be made to contact the Participant.

8 Study Procedures

8.1 Visit 1 (Screening and Enrollment up to the day of surgery)

- Review of medical record
- Informed Consent - Patients will be identified during their preoperative appointment and introduced to a study; they will be provided with a copy of the consent document and information about the study. The consenting will take place after additional discussion on the day of surgery.

8.2 Visit 2 (Randomization and Treatment – day of surgery)

- Induction of anesthesia is standardized to utilize lidocaine dose between 0.5 and 1 mg/kg, propofol between 1 and 1.5 mg/kg, and rocuronium at 0.6 mg/kg. Anesthesia will be maintained with sevoflurane at 1 minimum alveolar concentration (MAC) through the

induction and intubation sequence. Following induction but prior to rocuronium administration, TetraGraph will be calibrated, and the supramaximal current will be obtained as per standard of care practice.

- Prior to induction of anesthesia, the TetraGraph will be placed on the same arm as the IV catheter over the ulnar nerve and the thumb to measure the response of adductor pollicis nerve.
- Randomization will be performed utilizing REDCap and patients will be assigned to be intubated at TOFC=1 or 2 minutes after rocuronium administration.
- After NMBA administration, sets of measurements will be taken every 20 sec until the desired level of neuromuscular blockade has been reached or 2 minutes has passed since rocuronium administration, depending on the group. Once the level of blockade has been achieved or the appropriate time has lapsed, anesthesia providers will intubate the patient using video laryngoscopy.
- If the anesthesia team finds the intubating conditions to be unacceptable, bag mask ventilation will be continued until the anesthesiologists deems it appropriate to attempt laryngoscopy as per standard of care.
- Following intubation, perioperative care will be at the discretion of the anesthesiologist.
- When convenient for the anesthesia team, they will be surveyed about the ease of laryngoscopy. An independent observer will note the other 2 objective components of the survey.

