9.1 Sample Size Determination

Based on preliminary data, intubating score of 3 (ideal conditions) will occur in approximately 65% of patients in the two-minute group. With a sample size of 83 patients per group (166 patients total), we will have 80% power at the 5% significance level to detect a difference in this outcome of 20% (i.e. 65% vs. 85%) between the two-minute group and the other two treatment groups using a chi-square test. We will enroll 85 patients in each group (170 total) to account for possible dropouts.

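### Laryngoscopy may be deferred past the randomised trigger in either arm, and no rule says how a deferred patient is scored, so a failure at the trigger can enter the primary analysis as ideal

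*Combined protocol and SAP*

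**What the plan says.** Section 5 sets the primary objective: "Compare intubating conditions when patients are intubated at 2 different endpoints: TOFC=1 or 2 minutes after administration of rocuronium at 0.6 mg/kg". Section 8.2 tells the team to intubate once the assigned trigger is reached. It then adds a safety provision: if conditions are found unacceptable, "bag mask ventilation will be continued until the anesthesiologists deems it appropriate to attempt laryngoscopy as per standard of care". The provision is not limited to one arm and sets no time or depth of block for the later attempt.

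On when the grade is taken, Section 4.1 says: "The assessment will be done using video laryngoscopy display at the time of intubation". It also says: "The time to intubation will be recorded". Under Section 8.2 the team is asked about ease of laryngoscopy afterwards, when convenient, and an independent observer notes the other two components.

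Table 17.1 has three items: laryngoscopy, cord position, and reaction to the tube and cuff. One poor quality makes the whole grade Poor, which is not clinically acceptable. Section 9.1 powers the trial on the share of patients with score 3, to "detect a difference in this outcome of 20% (i.e. 65% vs. 85%) between the two-minute group" and its comparator. Section 9.1.1 names a chi-square test.

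Sections 6.4, 9.1.1, 9.1.2 and 9.2 and Table 17.1 do not mention a deferred patient.

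**The concern.** The trial asks how good conditions are at the trigger. For a deferred patient, the plan read literally records how good they were at a later time chosen by the anesthesiologist, under deeper block. A patient whose jaw or cords were unacceptable at TOFC=1 or at 2 minutes can then be entered as score 3, the best possible result.

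Another reading is that a deferred patient has no valid score. Section 9.1.2 would then treat the score as missing and enrol a replacement, which removes the trigger failure altogether.

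The gap concerns only problems noticed before the tube goes in. Coughing or movement on tube insertion, which Section 4.2 describes as "evidenced by coughing or movement of the limbs following intubation", comes after the decision to proceed and is scored as intended.

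At stake is the meaning of the primary comparison. Depending on how deferral falls between the arms, a real difference can be diluted, or one can appear or be exaggerated.

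**Working it through.** **Inputs from the plan (Section 9.1):** score 3 in 65% (two-minute arm) and 85% (comparator); 5% significance level; 80% power; 83 per group, 85 enrolled per group. The level is taken as two-sided, which the plan does not state.

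**Assumed inputs, not in the documents:** d0 and d1, the shares of all patients deferred in the two-minute and TOFC=1 arms; f0 and f1, the shares of those deferred patients who are later scored 3. Deferred patients are taken to be non-ideal at the trigger.

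**Step 1. The plan's own figure.** With p0 = 0.65, p1 = 0.85 and mean 0.75:

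n = [1.960 × √(2 × 0.75 × 0.25) + 0.842 × √(0.65 × 0.35 + 0.85 × 0.15)]² / 0.20² = 72.4, so 73 per group without a continuity correction.

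With the correction, n' = (n/4) × [1 + √(1 + 4/(n × 0.20))]² = 82.1, so 83 per group. The stated 83 is reproduced by the corrected two-sided test. Section 9.1.1 does not say which version will be used, so both are shown below.

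**Step 2. Bias formula.** Recorded ideal rate in an arm = rate at the trigger + f × d. Hence

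bias in the difference (TOFC=1 minus two-minute) = f1 × d1 − f0 × d0.

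**Step 3. Uniform practice, planned effect true.** Suppose 20% of non-ideal patients in each arm are deferred and all later score 3 (f = 1, an upper bound).
- Two-minute: d0 = 0.20 × 35% = 7%; recorded 65% + 7% = 72%.
- TOFC=1: d1 = 0.20 × 15% = 3%; recorded 85% + 3% = 88%.
- Bias = 3 − 7 = −4 points; the difference falls from 20 to 16 points.

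**Step 4. No true difference.** Take 65% at the trigger in both arms, 5% deferred in one arm and 10% in the other, and f = 0.5 in both. Recorded rates are 65% + 2.5% = 67.5% and 65% + 5% = 70%, a bias of 2.5 points.

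**Step 5. Rare deferral, no true difference.** Take no deferral in one arm, 2% in the other, and f = 0.5. Recorded rates are 65% and 66%, a bias of 1 point.

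**Results.** Exact binomial enumeration, 85 per arm, two-sided chi-square at 5%:

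| Case | Quantity | Uncorrected | Corrected |
|---|---|---|---|
| 65% vs 85%, no deferral | power | 86.8% | 82.0% |
| Step 3: 72% vs 88% | power | 76.0% | 68.8% |
| 65% vs 65%, no deferral | significant, one given direction | 2.4% | 1.7% |
| Step 4: 67.5% vs 70% | significant, favouring the arm that defers more | 5.4% | 3.8% |
| Step 5: 65% vs 66% | significant, favouring the arm that defers more | 3.3% | 2.3% |

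**The case against.** **The scale already has a category for this patient.** Section 8.2 speaks of unacceptable conditions, and Table 17.1 has a matching Poor category that one poor item triggers. If laryngoscopy is tried at the trigger and meets active resistance or closed cords, Poor is the natural grade, and it would preserve the failure. This stands as a sensible reading. The plan does not require a first-look grade or say that it prevails over a later one. The wording of Section 8.2 also allows deferral before any laryngoscopy, in which case no first-look grade exists.

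**Late intubations can be found afterwards.** Time to intubation is to be recorded, and Table 17.2 has time to TOFC=1, so many could be identified. But a time does not give the reason for a delay, and no rule says what to do with the score. Settling that later, in an open-label trial, means choosing the primary outcome with results in view. The absence of a deferral field from Table 17.2 is weak evidence either way: the table also lacks the time to intubation promised in Section 4.1, so it is not a complete list.

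**Deferral may be rare.** It requires unacceptable conditions, a narrower group than non-ideal, because Good is non-ideal yet clinically acceptable. No rate of Poor is given. Step 5 shows how little a small imbalance does. This stands.

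**Stronger readings that the documents do not support.** A reader might infer that the bias always favours the arm that defers more. That needs equal f: 5% deferred with f = 1 adds 5 points, while 8% deferred with f = 0.5 adds only 4. A reader might also infer that equal deferral is harmless. That holds for equal shares of all patients with equal f, but not for equal shares of non-ideal patients, as Step 3 shows. Nor can one say which arm gains. Section 4.3 warns "Intubating the trachea at a TOFC=1 could result in conditions that suboptimal with movement of the vocal cords", but also says "the current standard of care involves intubating once about two minutes has elapsed and movement of the vocal cords is commonly seen".

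**Conclusion.** The concern holds as a gap in the outcome definition. Following the plan as written, a patient judged unacceptable at the trigger on jaw or cords can be recorded as score 3, unless a first-look Poor is taken and kept. For such patients the primary comparison does not measure TOFC=1 against 2 minutes.

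Size and direction cannot be determined from the documents. The figures rest on assumed deferral rates. The Step 3 loss of about 11 points of power uncorrected (86.8% to 76.0%), or 13 corrected (82.0% to 68.8%), is an upper bound for 20% uniform deferral of non-ideal patients, because it has every deferred patient later scoring 3. The inflation in Step 4 is modest.

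The planned 83 per group is not in dispute. This should be corrected, but it does not undermine the design.

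**What to change.** Keep the safety provision. In Sections 6.4, 8.2 and 9:

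- Define the primary outcome at the randomised trigger (first attempt) in both arms.
- Count any patient deferred because conditions were unacceptable as not ideal and not clinically acceptable, whatever the later grades, and keep that patient in the analysis without replacement.
- Record deferral (yes/no) and its reason in REDCap. If laryngoscopy was tried, grade jaw and cords at that first look.
- Use time to intubation and time to TOFC=1 to check for unreported deferrals.
- Report the number and percentage deferred by arm, with the difference and 95% CI.
- Give the analysis on grades at actual intubation as a sensitivity analysis.

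The cost is two REDCap fields and a few sentences, with no extra patients. The downside is that deferral is an open-label judgement, which could be used more readily in one arm and would override later grades, including the two components noted by the independent observer. The recorded reason and the sensitivity analysis limit this but do not remove it.
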